3. TRIAL PARTICIPANT DISPOSITION

3.1. DISPOSITION OF PARTICIPANTS

All of the participants who screened for and entered the study will be accounted for in a CONSORT flow diagram stratified by cohort (high vs. low risk) including the following measures:

The numbers of participants screened, screened out (with reasons for exclusion), enrolled, randomized, allocated to each study arm (with reasons for not receiving assigned intervention), reasons for discontinuation from follow-up (e.g., lost to follow-up, adverse event, noncompliance, etc.), and the number of participants with available data for each endpoint.

3.2. TREATMENT EXPOSURE

Self-reported pill taking will be reported by prescribed dosing day stratified by arm and overall. The summary measures will be number of doses taken and number of doses taken divided by

Confidential

number prescribed. The number and proportion of compliant participants will be reported by day and overall time.

4. EFFICACY/EFFECTIVENESS ANALYSES

4.1. EFFICACY ANALYSES

All efficacy analyses will be adjusted for age, sex at birth and time from symptom onset to enrollment. These adjustments will be additive unless otherwise specified.

All analyses will account for the household clustering using robust standard errors as available. If not available, bootstrap methods will be used.

For time to event analyses, baseline (time 0) will be day of the enrollment visit.

Endpoints will be summarized as number of participants: hospitalized without prior LRTI, hospitalized with prior LRTI, died without prior LRTI, died with prior LRTI, who meet LRTI definition. These will be shown as counts and percentages overall and by cohorts defined in Section 2.2 within further breakdown by arm.

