Participants will be assessed for study eligibility through a screening conducted through a web-based screening tool, HIPAA-compliant video conference (Telehealth), telephone, or text messaging.

Day 0 evaluations are as follows:

- Informed consent
- Collection of demographic information
- Sign HIPAA form
- Collection of past and current medical conditions, including known pregnancy and/or lactation status
- Collection of concomitant medication information
- Collection of information (including laboratory documentation of COVID-19 testing)
- Check of inclusion and exclusion criteria

Eligible participants will be randomized. Participants will receive a monitoring kit via courier, which will include thermometer and SpO₂ device. They will be instructed on how to self-assess respiratory rate. In addition, they will receive a swab kit via courier or mail, which includes a study instruction booklet, swabs, plastic tubes for swab collection, a return box with affixed Category B UN3373 label, as required by International Air Transport Association (IATA) guidelines ([UN3373 Medical Packaging 2020](#)), and a pre-paid return shipping label.

The participant will do the following on Day 1:

- Collect mid-nasal swab for PCR
- Complete Daily Survey (online, telephone, or text messaging). This survey will include confirmation of adherence to study therapy dosing and daily swab collection, concomitant medication review, AEs, and symptoms review and objective measures including SpO₂, respiratory rate, temperature, pulse, and ECG*. In addition, the modified inFLUenza patient-reported outcome (Flu-PRO) survey will be completed.
- Take study therapy (LPV/r or placebo [ascorbic acid]), as assigned
- *May collect DBS sample for analysis of HCQ, azithromycin, and LPV/r concentrations.*

Instructions for skin puncture and DBS sample preparation are provided in [Appendix 9](#). A study team member will be available via Telehealth, telephone, or text messaging to provide support for completion of this study procedure.

Screening (Day 0) and Day 1 procedures can occur on the same day.

The SARS-CoV-2 positive test results will be confirmed through laboratory records or through detailed description of testing as described by participant.

9.2. Day 2 Through Day 13

The participant will do the following every day from Day 2 through Day 13, inclusive:

- Collect mid-nasal swab for PCR
- Take study therapy until Day 10 (inclusive) for LPV/r, or ascorbic acid (as assigned)

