The Statistical Analysis Plan will be developed and finalized before database lock and will describe the participant populations to be included in the analyses, the detailed analytical plans with endpoints and procedures for accounting for missing, unused, and spurious data. An Interim Monitoring Plan will also be developed to describe approaches for re-estimation of sample size and any planned interim analyses. This section presents a brief summary of the planned statistical analyses of the primary and secondary endpoints (these are listed in [Section 4](#)).

11.3.1. *Efficacy Analyses*

Demographic characteristics (age, sex, race) of each study group will be tabulated.

The mean age (plus range and standard deviation) by sex of the enrolled participants, as a whole and per group, will be calculated.

Primary analyses: The primary analyses will be conducted on the intend-to-treat population overall and by cohort (high-risk and low-risk). Participants randomized to each active treatment will be compared to participants randomized to placebo (ascorbic acid). If appropriate, the primary analysis will make use of all participants randomized to placebo, whether contemporaneously enrolled or not, using an Empirical Bayesian information borrowing method (described below). Due to anticipated heterogeneity in risk of disease progression, pre-specified baseline variables, including age, BMI, and days of symptoms at time of enrollment will be included in the model to increase precision.

Both primary endpoints will be analyzed using a Cox proportional hazards model with robust standard errors, adjusted for within household correlation.

As-treated analysis: The primary analyses will be repeated, replacing randomization arm by actual treatment to account for possible off-label use of and noncompliance to the investigational products.

Subgroup analyses: All subgroup analyses will be pre-specified in the Statistical Analysis Plan. Any further subgroup analyses will be considered ad hoc.

Missing Data

Due to the design of the study and retention activities, measurable outcomes are expected for all participants. However, in the unlikely event of a missing test result, the missing data will be imputed.

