4.1.1. LRTI objective

Objective: To test the efficacy of HCQ and HCQ + azithromycin compared to placebo to prevent progression to LRTI, among persons with SARS-CoV-2 infection who are at high risk of progression.

Outcome: LRTI, defined by resting SpO₂<93%, sustained for 2 readings 2 hours apart AND presence of subjective dyspnea or cough within the first 14 days of follow-up.

Cohorts: mITT LRTI Cohort

Data Sets: HCQ LRTI Efficacy Data Set, HCQ+A LRTI Efficacy Data Set

Definition of Endpoint: A participant will be defined as having the endpoint if they have two resting SpO₂ readings less than 93% two hours apart but not more than 48 hours apart AND report subjective dyspnea (defined as a response of “somewhat or higher” on the “trouble breathing” question on flupro) or cough (defined as “somewhat or higher” as self-reported wet or dry cough) within 24 hours of the time the SpO₂ is reported during the first fourteen days of follow-up. The event time will be recorded as the day of the first SpO₂ reading less than 93% with the presence of subjective dyspnea or cough. Participants who do not reach this endpoint will be censored at the last time that the endpoint was ascertained not to be present. Hospitalization or death due to COVID-19 may be a competing risk. Per FDA guidance, participants who are hospitalized or die due to COVID-19 will have an event time that is the first of LRTI, hospitalization or death.

Analysis Details:

Kaplan-Meier cumulative incidence curves will be estimated and plotted for each intervention including 95% confidence intervals accounting for household cluster.

Cox proportional hazards models stratified by site and adjusted for baseline covariates identified above will be used to estimate the efficacy as 1 minus the hazard ratio. Due to potential clustering induced by the household design, robust standard errors will be estimated for the hazard ratio. The overall efficacy will be tested using a p-value ascertained from the Wald statistic based on

Confidential

the robust standard error. 95% confidence intervals will also be calculated based on the robust standard error. If there are too few endpoints to fit a Cox model then the proportion of participants meeting the endpoint in the first 14 days will be reported. Each active arm will be compared to the control arm separately using Fisher's Exact test.

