4.1.3. Duration of Shedding Objective

Objective: To separately estimate and test the efficacy of HCQ and HCQ + azithromycin placebo to reduce SARS-CoV-2 viral shedding in high and low risk participants combined.

Outcome: Time to clearance of nasal SARS-CoV-2, defined as 2 consecutive negative swabs (swabs collected daily Day 1 through Day 14).

Cohort: mITT Viral Shedding Cohort

Data sets: HCQ VS Data Set, HCQ+A VS Data Set

Endpoint: The endpoint time will be set as the day of the first negative swab. Hospitalization and death are also competing risks for this outcome; however, clearance is a positive outcome whereas hospitalization and death are negative outcomes that may impede our ability to detect clearance. Participants who are hospitalized or die will have their event time censored at day 14. Other participants who do not have 2 consecutive negative tests will be censored on the day of their last positive test.

Analysis details:

Same as Section 4.1.1.

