7.4. MAGNITUDE OF VIRAL SHEDDING

Objective: To test whether HCQ or HCQ + azithromycin is associated with decreased viral shedding from self-collected nasal swabs over 14 days compared to placebo

Outcomes: Quantity of SARS-CoV-2 detected from mid-nasal swabs by PCR as measured by cycle threshold (Ct)

Cohort: mITT Cohort

Data sets: VS Data Set

Analysis details: Generalized linear mixed effects models with random intercepts and slopes (time) will be used to model the quantity of SARS-CoV-2 over time. Because of the high number of samples where Ct was above the upper limit (eg >40) and not recorded, we will do analyses with Ct dichotomized as follows:

- Ct>40 on both targets vs Ct<=40 on either target
- Concordant results vs discordant or negative
- Ct<24 on either target as this may be an indicator of greater propensity to be infectious[2].

Fixed effects will include randomization arm, B-spline coefficients for time, an interaction between arm and time, cohort, age, and other baseline covariates indicated for the primary analysis. Time will be the time since enrollment visit to collection of the sample.

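### The co-primary viral-clearance Cox model omits Day 1 viral load, which is already collected; the test stays valid but forgoes power

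*SAP*

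**What the plan says.** **Clearance model.** SAP 4.1 states: "All efficacy analyses will be adjusted for age, sex at birth and time from symptom onset to enrollment". For shedding, SAP 4.1.3 gives only "Same as Section 4.1.1". That section specifies "Cox proportional hazards models stratified by site and adjusted for baseline covariates identified above", with robust standard errors. The p<0.10 imbalance rule in SAP 2.1 works on a list of age, sex, risk factors, race/ethnicity and time since symptom onset, so it cannot bring viral load in.

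**Protocol.** Section 11.3.1 says that "pre-specified baseline variables, including age, BMI, and days of symptoms at time of enrollment will be included in the model to increase precision". The list is open, but viral load is not on it.

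**Day 1 data.** Protocol 9.1 lists "Collect mid-nasal swab for PCR" first among the Day 1 tasks, ahead of study therapy, but sets no rule that the swab must come before the dose. SAP 2.2 uses the Day 1 and Day 2 swabs to remove participants who are already clear.

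**Quantity model.** SAP 7.4 states: "Generalized linear mixed effects models with random intercepts and slopes (time) will be used to model the quantity of SARS-CoV-2 over time". It continues: "Fixed effects will include randomization arm, B-spline coefficients for time, an interaction between arm and time, cohort, age, and other baseline covariates indicated"; the covariates meant are those of the main efficacy models. On the time scale it says: "Time will be the time since enrollment visit to collection of the sample". It does not say whether the Day 1 sample is an outcome. SAP 7.2, by contrast, explicitly leaves Day 1 out for Flu-PRO.

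**Scope.** The SAP covers the first three arms (HCQ, HCQ + azithromycin, control). The documents contain no SAP for LPV/r.

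**The concern.** The endpoint is time to two consecutive negative PCR swabs. The starting value of the same measurement is the obvious predictor of that time, and more direct than age, sex, BMI or symptom duration. The protocol's stated reason for adjusting is precision, yet the most direct candidate is missing. The covariate list looks carried over from the LRTI model without being rethought for a virologic endpoint.

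Leaving a prognostic covariate out of a Cox model moves the estimated HR towards 1, relative to the effect at a given covariate value, and gives up power. At stake is efficiency on the more objective of the two co-primary endpoints.

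**Working it through.** **1. Reproduce the planned events.** SAP 1.5.2 gives HR 1.6, 90% power, 1-sided 2.5%, and 200 events per pairwise comparison. SAP 1.4 gives 1:1 within a pair.
- Schoenfeld: 4(1.960+1.282)²/(ln 1.6)² = 42.03/0.2209 = 190.3, so 191.
- With five O'Brien-Fleming looks (SAP 1.5), simulated inflation is 1.024 (efficacy only) to 1.086 (symmetric binding futility), giving 195 to 207.
- Freedman: 10.51 × (2.6/0.6)² = 197.3, so 198.
- Fixed-design power at 200 events: Φ(√200 × 0.470/2 − 1.960) = Φ(1.363) = 91.4%.
- Control clearance by Day 14 with a 10-day median: 1 − 2^(−1.4) = 62.1%, matching the 62% in Protocol 11.1.2.

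So 200 events follow from a calculation without covariates.

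**2. Clearance model, 1.6 taken as the effect at a given viral load.** Exponential times, censoring at Day 14, about 284 to 294 participants for 200 events, 1500 runs per scenario. The model has arm and symptom duration, without or with Day 1 load. **Assumed, not in the documents:** the fold change in clearance hazard per SD of load, and a correlation of load with symptom duration of 0 or −0.5. Ranges span the two correlations.

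| Fold change per SD | HR without | HR with | Power without | Power with |
|---|---|---|---|---|
| 1.0 | 1.60 | 1.60-1.61 | 90.7-91.6% | 90.5-91.6% |
| 1.25 | 1.59 | 1.61 | 90.1-90.3% | 91.1-91.7% |
| 1.5 | 1.55-1.56 | 1.60-1.61 | 87.1-88.3% | 91.5-91.7% |
| 2.0 | 1.47-1.50 | 1.60-1.61 | 77.0-79.9% | 90.8-91.3% |
| 2.5 | 1.41-1.45 | 1.59-1.61 | 69.3-74.2% | 89.0-90.7% |

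Monte Carlo error is about 0.8 points at 90% (√(0.9×0.1/1500)). The first row shows that adding a covariate with no prognostic value costs nothing visible.

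**3. Clearance model, 1.6 taken as the effect without viral load in the model.** The conditional HR was raised to 1.615, 1.66, 1.79 and 1.93, so that the unadjusted HR is about 1.6 (obtained: 1.60 to 1.68).

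| Fold change per SD | Power without | Power with |
|---|---|---|
| 1.25 | 89.6-91.0% | 90.9-92.3% |
| 1.5 | 91.1-92.4% | 93.7-95.4% |
| 2.0 | 92.1-94.0% | 97.9-98.3% |
| 2.5 | 92.9-94.7% | 99.6-99.7% |

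**4. LPV/r design (Protocol synopsis and 11.1.1).** 173 per arm, conditional HR 1.5, 60% control clearance by Day 14, 5% dropout, whole-day times, 600 runs. For an assumed log HR per SD of 0.3 / 0.5 / 0.7 (1.35- / 1.65- / 2.0-fold), the unadjusted HR is 1.48 / 1.44 / 1.41 and power 83% / 79% / 70%. Adjusted, the HR is about 1.50 and power 85-87%. These inputs yield more events than the plan's 2 × 99 = 198: active clearance is 1 − 0.4^1.5 = 74.7%, so events are 346 × 0.95 × (0.60 + 0.747)/2 ≈ 221. That gives about 85% power before any covariate matters. The shortfall against the stated 80% is therefore none, 1 point and 10 points.

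**5. Quantity model (SAP 7.4).** Logistic random-intercept model, n = 270, Days 2-14, linear time, random-intercept SD 2.0, arm effect −0.10 log-odds per day (true average −0.70), 150 runs. All of these are assumptions.

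| Share of between-person variance explained by Day 1 | Estimate without / with | SE without / with | Power without / with |
|---|---|---|---|
| 10% | −0.69 / −0.69 | 0.265 / 0.250 | 74% / 80% |
| 30% | −0.74 / −0.72 | 0.262 / 0.229 | 78% / 87% |
| 50% | −0.69 / −0.69 | 0.262 / 0.199 | 73% / 92% |

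The arm-by-time test barely moves (91-92% without, 91-95% with).

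**Limits.** The simulations in steps 2, 3 and 5 ignore household clustering, site strata, ties and interim looks. Step 5 omits the random slope and the splines.

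**The case against.** The strongest reply is that nothing is wrong with the planned test. The shift of the HR towards 1 is non-collapsibility: the model without Ct estimates a different, legitimate quantity, and type I error is unaffected. That stands. A reader might infer that the estimate is biased, or that a chance imbalance in starting load invalidates the comparison; randomisation and the standard error already cover that.

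A reader might also infer that the design loses its 90% power. The documents do not say whether 1.6 is conditional on viral load. The 200 events reproduce without covariates, and on that reading planned power is kept (step 3).

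A third tempting inference is that SAP 7.4 suffers the same dilution, or models Day 1 as an outcome. Its participant-level random effects absorb the omitted covariate, and step 5 shows no dilution. The text does not say how Day 1 is treated, and keeping baseline among the outcomes is a recognised approach.

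Three practical objections also stand:
- Time from symptom onset is already adjusted for and recovers a small part of the loss (77.0% to 79.9% power at 2-fold).
- For the HCQ arms, enrolment stopped on 28 July 2020, and SAP 7.4 remarks on how many Ct values exceed 40. The Ct data therefore appear to have been seen, and a Ct covariate added now would be post hoc.
- Without a rule on swab timing, some Day 1 values could be post-treatment.

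The open list in Protocol 11.3.1 means that the LPV/r omission is not final. That is a reason to settle it before that SAP is written.

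**Conclusion.** The omission is real, and adjustment is a worthwhile efficiency gain that can be pre-specified for LPV/r. It is not a validity failure. If 1.6 is the effect at a given viral load, the power forgone at 200 events is about 1-2 points at 1.25-fold per SD, 3-5 points at 1.5-fold and 11-14 points at 2-fold. If 1.6 is the effect without viral load in the model, nothing planned is lost and adjustment adds about 1, 3 and 4-6 points at the same strengths. No single figure can be claimed, because prognostic strength is assumed throughout. For SAP 7.4 the conclusion is narrower: precision of the average arm effect is lost, and the handling of Day 1 is unspecified.

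**What to change.** - **LPV/r:** add Day 1 Ct (lower of the two targets) as a pre-specified covariate of the clearance Cox model, in Protocol 11.3.1 and in the LPV/r SAP before database lock.
- **Stopped HCQ arms:** run the same model as a documented post-hoc sensitivity analysis, leaving the planned analysis as primary.
- **Coding:** give not detected (Ct above 40) and missing separate categories or indicators. One shared code would mix low with unknown viral load.
- **Timing:** count a Day 1 swab as baseline only if taken before the first dose, and treat later ones as missing.
- **SAP 7.4:** state whether Day 1 is a covariate, with outcomes from Day 2 onward, or an outcome with a common baseline mean across arms. It should not be both.

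Cost: a few sentences and a few extra model terms, with no new visits or samples. The reported HR becomes conditional on viral load, which the report should say.

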4.1.1. LRTI objective

Objective: To test the efficacy of HCQ and HCQ + azithromycin compared to placebo to prevent progression to LRTI, among persons with SARS-CoV-2 infection who are at high risk of progression.

Outcome: LRTI, defined by resting SpO₂<93%, sustained for 2 readings 2 hours apart AND presence of subjective dyspnea or cough within the first 14 days of follow-up.

Cohorts: mITT LRTI Cohort

Data Sets: HCQ LRTI Efficacy Data Set, HCQ+A LRTI Efficacy Data Set

Definition of Endpoint: A participant will be defined as having the endpoint if they have two resting SpO₂ readings less than 93% two hours apart but not more than 48 hours apart AND report subjective dyspnea (defined as a response of “somewhat or higher” on the “trouble breathing” question on flupro) or cough (defined as “somewhat or higher” as self-reported wet or dry cough) within 24 hours of the time the SpO₂ is reported during the first fourteen days of follow-up. The event time will be recorded as the day of the first SpO₂ reading less than 93% with the presence of subjective dyspnea or cough. Participants who do not reach this endpoint will be censored at the last time that the endpoint was ascertained not to be present. Hospitalization or death due to COVID-19 may be a competing risk. Per FDA guidance, participants who are hospitalized or die due to COVID-19 will have an event time that is the first of LRTI, hospitalization or death.

Analysis Details:

Kaplan-Meier cumulative incidence curves will be estimated and plotted for each intervention including 95% confidence intervals accounting for household cluster.

Cox proportional hazards models stratified by site and adjusted for baseline covariates identified above will be used to estimate the efficacy as 1 minus the hazard ratio. Due to potential clustering induced by the household design, robust standard errors will be estimated for the hazard ratio. The overall efficacy will be tested using a p-value ascertained from the Wald statistic based on

Confidential

the robust standard error. 95% confidence intervals will also be calculated based on the robust standard error. If there are too few endpoints to fit a Cox model then the proportion of participants meeting the endpoint in the first 14 days will be reported. Each active arm will be compared to the control arm separately using Fisher's Exact test.

4.1.2. Hospitalization/Death objective

Objective: To test the efficacy of HCQ, HCQ + azithromycin, or LPV/r compared to placebo to prevent hospitalization and death measured at Day 28 among participants who are at high risk of progression

Outcome: COVID-19 related hospitalization or death at or before day 28 or follow-up

Cohort: mITT High Risk Cohort

Data sets: HCQ Efficacy Data Set, HCQ+A Efficacy Data Set

Definition of Endpoint: A participant will be defined as having the endpoint if they were hospitalized or died due to COVID-19 as determined by the adjudication committee before day 28.

Analysis Details:

The proportion of participants with a hospitalization or death before the end of planned follow-up will be reported. Each active arm will be compared to the control arm separately using Fisher's Exact test.

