1.1. GENERAL DESIGN CONSIDERATIONS

1.2. STUDY OBJECTIVES AND ENDPOINTS

The protocol was written early in the pandemic when there was not adequate information about typical disease course. Between then and the writing of this document, our understanding of COVID-19 disease progression has changed, resulting in changes to some of the objectives and endpoints. Most notably, the trial was stopped early for operational futility on the primary clinical objectives. These changes are noted in the table below.

Table 1 Original objectives and endpoints as written in the protocol

Objectives	Endpoints
Primary	
To test the efficacy of HCQ and HCQ + azithromycin compared to placebo to prevent progression to LRTI, among persons with SARS-CoV-2 infection who are at high risk of progression	LRTI, defined by resting SpO ₂ <93%, sustained for 2 readings 2 hours apart AND presence of subjective dyspnea or cough
To test the efficacy of HCQ and HCQ + azithromycin compared to placebo to prevent hospitalization and death measured at Day 28 among participants who are at high risk of progression	Cumulative incidence of hospitalization or mortality, measured at Day 28
To test the efficacy of HCQ and HCQ + azithromycin compared to placebo to reduce SARS-CoV-2 viral shedding	Time to clearance of nasal SARS-CoV-2, defined as 2 consecutive negative swabs (swabs collected daily Day 1 through Day 14)
Secondary	
1. To test the safety of HCQ and HCQ + azithromycin compared to placebo for	Serious adverse events (including death and hospitalization) and adverse events resulting in treatment discontinuation

treatment of high-risk outpatients with SARS-CoV-2 infection	
2. To test whether HCQ and HCQ + azithromycin has an effect on the duration of hospitalization among persons who become hospitalized with COVID-19 disease	Days of hospitalization
3. To test whether HCQ and HCQ + azithromycin has an effect on disease severity compared to placebo	
 Peak score on WHO Ordinal Scale for Clinical Improvement Peak score on modified Flu-PRO within the first 14 days
4. To test whether HCQ and HCQ + azithromycin decreases the resolution rate for symptomatic SARS-CoV-2 infection/COVID-19 disease compared to placebo	
 Proportion of days with fever after randomization Proportion of days with respiratory symptoms after randomization Proportion of days with SpO₂<93% without supplemental oxygen after randomization

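### SAP 4.1 requires covariate adjustment and household clustering in all efficacy analyses, but the hospitalization/death objective and the LRTI fallback plan only Fisher's exact test, with no contrast or interval

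*SAP*

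**What the plan says.** SAP 4.1 sets two general rules. On covariates: "All efficacy analyses will be adjusted for age, sex at birth and time from symptom onset to enrollment". On households: "All analyses will account for the household clustering using robust standard errors as available", followed by "If not available, bootstrap methods will be used". The qualifier that closes the covariate rule concerns whether the adjustments are additive, not whether to adjust.

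SAP Table 1 lists, under the primary objectives, "Cumulative incidence of hospitalization or mortality, measured at Day 28". SAP 4.1.2 gives the whole analysis of it in two sentences: "The proportion of participants with a hospitalization or death before the end of planned follow-up will be reported", and then "Each active arm will be compared to the control arm separately using" Fisher's exact test. It names no covariate, household method, effect measure or interval.

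SAP 4.1.1 (LRTI) has a Cox model with covariates, robust standard errors and a 95% interval, but its sparse-event branch falls back to the same analysis: "If there are too few endpoints to fit a Cox model then the proportion of participants" with the endpoint is reported and the arms are compared by Fisher's test.

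Protocol 7.5 randomises by household. SAP 2.1 recognises this for the baseline table, where it prescribes GEE with exchangeable correlation within household.

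**The concern.** The general rule and the specific sections conflict, and nothing in 4.1.2 says that the departure is deliberate. Fisher's test treats two members of one household, who could only have been assigned together, as two independent assignments. As the SAP stands, the baseline table gets better household handling than a primary outcome.

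The missing interval matters more. SAP 1.3 reports very few hospitalizations. A test on a handful of events may be unable to reject whatever the data show, and a bare non-significant p-value is easily read as no effect. An interval would show which benefits and harms remain possible.

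**Working it through.** **Inputs from the documents.** Alpha 0.05 (SAP 2), two-sided (Protocol 5.1); 165 per arm, 30% control rate, 5% dropout, 50% efficacy, 90% power and 93 events per comparison (SAP 1.5.1); four interim looks and one final (SAP 1.5).

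**Not in the documents, so assumed.** Household correlation (ICC), the share of participants in shared households, the event count, and any arm size other than 165.

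**1. The plan's own figure.** Events for a hazard ratio of 0.5 in a fixed design: 4(1.960 + 1.282)² / (ln 0.5)² = 87.5, so 88. Five O'Brien-Fleming looks raise this to about 90 (efficacy bound only) or 95 (efficacy and futility bounds). The stated 93 lies in that range. With the risk halved, 93/1.5 = 62 control events and 31 per active arm; 62 + 31 + 31 = 124, as the SAP states. The event target is not in dispute here.

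**2. Rule against section.**

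| Requirement | 4.1 | 4.1.1 main | 4.1.1 fallback | 4.1.2 |
|---|---|---|---|---|
| Covariates | all efficacy analyses | yes | none | none |
| Household clustering | all analyses | robust SE | none | none |
| Contrast with 95% interval | not stated | yes | none | none |

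**3. True size of Fisher's test, independent participants.** Sum the binomial probabilities of every 2x2 table with two-sided p ≤ 0.05, with equal risk in both arms.

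| Per arm | Event risk | Size |
|---|---|---|
| 165 | 30% | 0.038 |
| 165 | 5% | 0.026 |
| 165 | 2% | 0.014 |
| 75 (assumed) | 5% | 0.015 |
| 75 (assumed) | 3% | 0.006 |

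**4. Size when clustering is ignored (simulation).** Two-person households are assigned to the same arm, 165 per arm, ICC 0.5. Design effect = 1 + share × ICC, where share is the proportion of participants living in such pairs.

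| Share in pairs | Design effect | Size at 30% risk | Size at 5% risk |
|---|---|---|---|
| 0 | 1.00 | 0.038 | 0.025 |
| 20% | 1.10 | 0.049 | 0.033 |
| 40% | 1.20 | 0.058 | 0.041 |
| 100% | 1.50 | 0.092 | 0.070 |

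The discreteness of the exact test pulls the size down and ignored clustering pushes it up. Under light clustering the size stays at or below 0.05; under heavy clustering it goes above.

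**5. What very few events do to the test.** Five events against none gives p = 0.058 at 75 per arm and 0.061 at 165 per arm. Five events in a comparison therefore cannot produce p < 0.05.

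**6. What an interval adds.** Take 2/75 against 4/75 (assumed counts). The risk difference is 2.7% − 5.3% = −2.7 points. The Wilson limits are 0.7% to 9.2% and 2.1% to 12.9%, which give a Newcombe 95% interval of about −10.5 to +4.6 points. Neither benefit nor harm is excluded.

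**7. Cost of allowing for clustering.** At the design rates with about 157 evaluable per arm (165 × 0.95), 30% against 15%: SE = √(0.3×0.7/157 + 0.15×0.85/157) = 0.0464, so −15 points with a 95% interval of −24.1 to −5.9. With an assumed design effect of 1.2 the SE is 0.0464 × √1.2 = 0.0508, and the interval is −25.0 to −5.0.

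**8. Whether the bootstrap named in 4.1 would supply the interval.** With 75 per arm and independent participants, the percentile-bootstrap 95% interval for the risk difference covers about 88% of the time at 3% against 1.5%, and about 75% at 2% against 1%. At 3% against 1.5%, the chance that at least one arm has no events is 1 − (1 − 0.97^75)(1 − 0.985^75) = 1 − 0.898 × 0.678 = 39%. Such an arm contributes no bootstrap variability.

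**The case against.** The strongest reply is that an exact test is a reasonable choice for very few events, and that three covariates cannot be fitted to a handful of outcomes. That stands: the fault is an unstated exception to 4.1 and a missing interval, not the use of an exact test as such.

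The gap is also partly covered. SAP 4.1.1 counts COVID-19 hospitalization and death as events in the LRTI analysis, so those in the first 14 days enter an adjusted Cox model if one can be fitted. Arm counts and percentages are to be tabulated, so a crude difference can be worked out by hand. This stands too, but it covers neither the later events up to day 28 nor the fallback, and a hand-derived difference has no planned interval.

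Clustering may be light. The 4.1.2 cohort is high-risk only, so a clustered pair needs two members of a household who are both high-risk, symptomatic and newly positive. The larger shares in the table above are illustrations, not estimates.

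Two stronger readings are tempting and not supported. First, a reader might infer a breach of Protocol 11.3.1: "Both primary endpoints will be analyzed using a Cox proportional hazards model with robust standard errors, adjusted for within household correlation". Those endpoints are symptom resolution and viral clearance, adopted when the protocol replaced the earlier clinical endpoints (Protocol 4), so the sentence does not govern hospitalization/death. Second, a reader might infer that a household permutation test would recover worthwhile power. Any such gain depends on assumed household shares, covariate strength and event risks. In one simulation at a 3% control risk and an odds ratio of 0.3, power was about 1% for Fisher's test and about 11% for the adjusted permutation test. Neither could decide the objective.

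**Conclusion.** The point holds as a conflict within the SAP and a reporting gap. Section 4.1.2 and the fallback in 4.1.1 do not meet the covariate and household rules of 4.1, and they plan no contrast or interval.

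A reader might also conclude that Fisher's test is simply conservative here and that the false-positive rate is therefore safe. The documents do not support that. The size is 0.026 at 165 per arm and 5% risk, and 0.006 at an assumed 75 per arm and 3% risk, but only if participants are independent. With everyone in pairs and an ICC of 0.5 it is 0.070 at 5% risk and 0.092 at 30% risk (165 per arm). The documents give no ICC, household share or event count, so the net direction is unknown.

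The practical effect is limited, because enrollment stopped for operational futility on this objective. The result will still be tested and reported, and with so few events the interval is its informative part. The change is worth making; the analysis is not invalid without it.

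**What to change.** In SAP 4.1.2 and the fallback in 4.1.1:

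- Report the risk difference for each active arm against control with a 95% interval suited to few events (score or exact type), widened for clustering where household members share an arm. Do not use a percentile household bootstrap, which under-covers with rare events.
- Base the test on permuting the arm labels of whole households within the randomisation strata. Both analyses are confined to the high-risk cohort, so in practice this means within site. Include the 4.1 covariates only where event counts allow.
- Keep Fisher's exact test as a sensitivity check.

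In SAP 4.1, state that covariate adjustment is waived when events are too few, and give the criterion.

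The cost is a few sentences of SAP text, slightly more analysis work and a wider interval if households do cluster. No new data are needed.
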